13.0 DATA MANAGEMENT AND PROCEDURES

13.1 Design and Development

This protocol will utilize a centralized Data and Statistics center (DSC). The DSC will be responsible for the development of the case report forms (CRFs), development and validation of the clinical study database, ensuring data integrity, and training site and participating node staff on applicable data management procedures. Ideally, a web-based distributed data entry model will be implemented. This system will be developed to ensure that guidelines and regulations surrounding the use of computerized systems used in clinical trials are upheld. The remainder of this section provides an overview of the data management plan associated with this protocol.

13.1.1 Site Responsibilities

The data management responsibilities of each individual CTP will be specified by the DSC.

13.1.2 Data Center Responsibilities

The DSC will 1) develop a data management plan and will conduct data management activities, 2) provide final CRFs for the collection of all data required by the study, 3) provide data dictionaries for each CRF that will comprehensively define each data element, 4) conduct ongoing data validation and cleaning activities on study data from all participating CTPs through database lock.

13.2 Data Acquisition and Entry

Completed forms and electronic data will be entered into the data management system in accordance with the CRF Completion Guidelines established by the DSC. Only authorized individuals shall have access to electronic CRFs.

13.3 Data Editing

Data will be entered into the DSC automated data acquisition and management system. If incomplete or inaccurate data are found, a data clarification request will be generated and distributed to treatment programs for a response. Sites will resolve data inconsistencies and errors and enter all corrections and changes into the DSC automated data acquisition and management system. Data status reports ideally will be issued monthly to assist the site, the corresponding RRTC (node) and the lead investigator to monitor the site's progress in responding to queries.

13.4 Data Transfer/Lock

Data will be transmitted by the DSC to the NIDA central data repository as requested by NIDA. The DSC will conduct final data quality assurance checks and "lock" the study database from further modification. The final analysis dataset will be returned to NIDA, as requested, for storage and archive.

13.5 Data Training

The training plan for CTP staff includes provisions for training on assessments, CRF completion guidelines, and computerized systems.

13.6 Data QA

To address the issue of data quality, the DSC will follow a standard data monitoring plan. An acceptable data quality level prior to any database lock will be given as part of the data management plan. Data quality summaries will be made available during the course of the study.

14.0 PUBLICATIONS AND OTHER RIGHTS

Protocol development and implementation in the NIDA CTN is a collaborative process. The publication plan for the current protocol will comply with the CTN Publications Subcommittee's guidance on publications. Individuals making substantive contributions to the protocol development and implementation will have opportunities to participate in publications. Other contributors will also be acknowledged.

17.0 APPENDIX A

17.1 Definition of Adverse Event and Serious Adverse Event

Adverse Event: An adverse event (AE) is defined as any reaction, side effect, or untoward event that occurs during the course of the clinical trial, whether or not the event is considered study-related or clinically significant. A new illness, symptom, sign or worsening of a pre-existing condition or abnormality is considered an AE. A thorough history during the eligibility assessment phase should record any chronic, acute, or intermittent preexisting or current illnesses, diseases, symptoms, or laboratory signs of the participant, to avoid reporting pre-existing conditions as new AEs and to assist in the assessment of worsening in intensity or severity of these conditions that would indicate an AE. Stable chronic conditions, such as arthritis, which are present prior to clinical trial entry and do not worsen are not considered AEs. The AE form is used to capture reportable AEs (as defined in the protocol) and also used to record follow-up information for unresolved events reported on previous visits. A study investigator will identify and characterize each AE, and follow appropriate reporting procedures.

Serious Adverse Event (SAE): A serious adverse event is defined as any untoward physical or psychological occurrence during the study that suggests a significant hazard, side effect, or precaution will be defined as an SAE. This includes, but may not be limited to any of the following events:

- Death: A death occurring during the study or which comes to the attention of the investigator during the protocol-defined follow-up after the completion of therapy, whether or not considered treatment-related, must be reported.
- Life threatening: Any adverse therapy experience that places the participant or participants, in the view of the investigator, at immediate risk of death from the reaction as it occurred (i.e., it does not include a reaction that had it occurred in a more serious form, might have caused death).
- In-patient hospitalization or prolongation of existing
- Persistent or significant disability or incapacity,
- Congenital anomaly/birth defect.
- An event that required intervention to prevent one of the above outcomes.

Unexpected Adverse Event: Any adverse therapeutic experience, the specificity or severity of which is not consistent with the investigator brochure or the package insert. If neither is available then the protocol and consent are used to determine an unexpected adverse event.

Pregnancy: Pregnancies that occur on study (i.e., conception between randomization and study day 121) will be captured on a pregnancy CRF and not separately reported as an AE or SAE.

Laboratory Results: Laboratory results will be captured on specific laboratory CRFs. Those results that are considered clinically significant will also be reported as an AE.

Eliciting and Monitoring Adverse Events: Qualified research staff will elicit participant reporting of reportable AEs/SAEs at study assessment visit designated to collect AEs. Adverse events (medical and/or psychiatric) assessment will initiate with participant consent and follow-up will continue through 30 days post last active treatment visit. The research staff will obtain as much information as possible about the reportable AE/SAE to complete the AE/SAE forms and will consult with designated staff as warranted. Reportable SAEs will be reported as indicated below. A study investigator will review reportable AEs for seriousness, severity, and relatedness weekly. Appropriate site staff will review all reportable AE documentation and verify accuracy of assessments at least once weekly when the participant attends the CTP to ensure that all of these AEs are appropriately reported and to identify any unreported AEs that require reporting. Reportable AEs/SAEs will be followed until resolution or stabilization or study end, and any serious and study-related AEs will be followed until resolution or stabilization even beyond the end of the study. Each participating site's Protocol PI is responsible for study oversight, including ensuring human research subject

protection by designating appropriately qualified, trained research staff and medical clinicians to assess, report, and monitor adverse events.

Protocol monitors from the Clinical Coordinating Center (CCC) and local node staff will review the study sites and study data on a regular basis and will promptly advise sites to report any previously unreported safety issues and ensure that the reportable SAEs are being followed appropriately by the research staff. The node staff or CCC monitor will ensure that any unreported or unidentified reportable SAEs discovered during visits are promptly reported by the site to the Safety Monitor, NIDA, the Node or Protocol PI or designee, the lead investigator for the study and the IRB per local IRB requirements and will be reported on the monitoring report. Staff education, re-training or appropriate corrective action plan will be implemented at the participating site when unreported or unidentified reportable AEs or SAEs are discovered, to ensure future identification and timely reporting by the site. The NIDA CTN DSMB will also review data related to safety monitoring for this trial periodically at regularly scheduled meetings.

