6.5.3 Safety Measures

1. Adverse Events (AEs)

AEs will be assessed by study staff as outlined in Table 2. If an AE requires medical attention, it should be reported to a study medical clinician immediately.

2. The Hospital Anxiety and Depression Scale (HADS)

A potential side-effect of bupropion XL is anxiety (see section 8.7) and smoking cessation can be associated with symptoms of nicotine withdrawal, which includes depressed mood. In addition to AE assessments, the potential increase in depression and anxiety will be assessed with the Hospital Anxiety and Depression Scale (HADS; Zigmond and Snaith, 1983). The HADS is a brief, validated instrument that screens for both depression and anxiety (Bjelland et al. 2002) and will be completed following the schedule outlined in Table 2. Participants who score in the range for possible depression (total depression score of 8 or higher) or anxiety (total anxiety score of 8 or higher) should be assessed by a qualified clinician before leaving the clinic. If a participant is assessed and, at subsequent visits, continues to have the same elevated score then the need for reassessment is at the discretion of a qualified clinician; a subsequent increase in the HADS score would require assessment by a qualified clinician.

3. Suicide and Homicide Screening Form

Smoking cessation can be associated with symptoms of nicotine withdrawal, which includes depressed mood. The Suicide and Homicide Screening Form is a structured, reliable interview modified from the Psychiatric Research Interview for Substance and Mental Disorders- PRISM (Hasin, et al. 1996). This form will be completed by study staff according to the schedule outlined in Table 2. Participants reporting current suicidal/homicidal intent should be assessed by a qualified clinician.

4. Pregnancy Test and Birth Control Assessment

A urine pregnancy test designed to measure human chorionic gonodotropin hormone will be completed on study day 1, prior to randomization, and during study weeks 5 and 10. All female participants will be tested except women who have a documented hysterectomy. During screening/baseline, female participants' use of birth control and breastfeeding status will be assessed.

5. Prior/Concomitant Medications

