7.4 Active Treatment Phase

The active treatment phase is 10 weeks in duration. During this time, participants in both treatment conditions will participate in the substance-abuse treatment typically offered by the CTP. Participants randomized to the TAU+SCT arm will receive individual smoking-cessation counseling consisting of approximately one ten-minute counseling session per week during study weeks 1 through 10. In addition, all TAU+SCT participants will receive bupropion XL (300 mg/day) and, during the post-quit treatment phase, the nicotine inhaler (6-16 cartridges per day ad libitum). Finally, all TAU+SCT participants will receive contingency management in which drawings for prizes are given for smoking abstinence as assessed by carbon monoxide (CO) levels during the post-quit phase of the trial (i.e., weeks 4-10). The TAU+SCT participants will have a target quit smoking day at the end of study week 3. Following the final week 10 visit, TAU+SCT participants will be provided with a 3-day bupropion XL dose taper, in which 150 mg is taken once per day and with a 3 week nicotine inhaler taper. Participants in both conditions will meet with study staff twice weekly to complete study assessments as outlined in Table 2, with the constraint that visits ideally occur on nonconsecutive days.

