7.5 Follow-up

The follow-up visits will be conducted at approximately study weeks 16 and 28. The measures to be collected during this visit are delineated in Table 2. There will be a 21-day timeframe in which to complete each follow-up visit.

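### Conceptions are to be recorded up to study day 121, but no pregnancy test or pregnancy question is scheduled after week 10, leaving about 42% of the window to unprompted self-report

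*Protocol*

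**What the plan says.** Section 17.1 fixes a conception window and a form for recording it: "Pregnancies that occur on study (i.e., conception between randomization and study day 121) will be captured on a pregnancy CRF". The same sentence takes pregnancy out of ordinary safety reporting, because it is "captured on a pregnancy CRF and not separately reported as an AE or SAE".

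The detection steps are in section 6.5.3, item 4. The urine test "will be completed on study day 1, prior to randomization, and during study weeks 5 and 10". At screening/baseline only, "use of birth control and breastfeeding status will be assessed". Table 2 agrees: pregnancy tests in weeks 1, 5 and 10, and birth control assessment at screening/baseline alone.

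After treatment, section 7.5 says: "The follow-up visits will be conducted at approximately study weeks 16 and 28". For those visits Table 2 lists the urine drug screen, ASI-Lite follow-up, TLFB, RAB, BSCS, CO, FTND, locator information (week 16 only) and non-study smoking treatment. The pregnancy test, birth control, adverse event and concomitant medication rows are blank.

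For adverse events, section 17.1 says that "follow-up will continue through 30 days post last active treatment visit". They are elicited at visits designated for that purpose, and Table 2 marks these only at screening/baseline and in weeks 1-10.

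Study drug continues past the last treatment visit. Section 7.4 provides a 3-day bupropion XL taper, "in which 150 mg is taken once per day and with a 3 week nicotine inhaler taper".

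**The concern.** A rule that names a conception window needs some means of learning about conceptions across that window. Here the scheduled means stop at week 10 and the window runs seven weeks longer. From then on a site learns of a pregnancy only if the participant mentions it.

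Table 1 gives the unestablished safety of bupropion in pregnancy as the reason for both the contraception requirement and the pregnancy exclusion. Section 17.1 also lists congenital anomaly as a serious adverse event, and linking one to study drug requires knowing of the pregnancy and its approximate conception date. If the pregnancy CRF is filled in only when someone volunteers, the reported count may be too low, and a reader of the trial report could not tell. What is at stake is safety ascertainment, not the efficacy result.

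**Working it through.** **Inputs**

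- Window: randomization (study day 1) to day 121, i.e. 121 days (section 17.1).
- Active phase: 10 weeks, days 1-70, so week 10 is days 64-70 (section 7.4).
- Tapers after the final week-10 visit: bupropion XL 3 days, nicotine inhaler 3 weeks (sections 7.4, 8.10.1, 8.10.2).
- Adverse event follow-up: 30 days after the last active treatment visit (section 17.1).
- Follow-up visits: week 16 = days 106-112 and week 28 = days 190-196, each with a 21-day frame (section 7.5).

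**The plan's own figure.** The protocol does not derive day 121, but its durations reproduce it: 70 + 21 + 30 = 121. The window looks like the treatment phase, plus the inhaler taper, plus 30 days. This is an inference.

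**Part of the window after the last scheduled test**

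- Test on day 70: 121 − 70 = 51 days (71-121); 51/121 = 42%.
- Test on day 64: 121 − 64 = 57 days (65-121); 57/121 = 47%.
- Week-10 visit missed, last test in week 5 (day 35 at the latest): 121 − 35 = 86 days; 86/121 = 71%.

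**Study drug during the 51 days** (final week-10 visit on day 70; TAU+SCT arm only)

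- Bupropion taper: days 71-73, 3 days.
- Inhaler taper: days 71-91, 21 days including those 3; 21/121 = 17%.
- After all study drug: days 92-121, 30 days; 30/121 = 25%.

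**Does adverse event follow-up fill the gap?** It ends between day 64 + 30 = 94 and day 70 + 30 = 100, which is 121 − 94 = 27 to 121 − 100 = 21 days before the window closes. Table 2 has no visit between week 10 and week 16 (day 106 at the earliest), so no scheduled contact falls inside it. Even if it is counted generously as a prompt to day 100, days 101-121 remain: 21/121 = 17%.

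**Allowing for test lag.** A test cannot detect a very recent conception. The protocol gives no lag from conception to a positive urine test, so the lag below is an assumption. The test is taken on day 70.

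| Assumed lag (days) | Conception days not reached | Share of window | Of these, on bupropion | Of these, on any study drug |
|---|---|---|---|---|
| 0 | 71-121 (51) | 42% | 3 | 21 |
| 7 | 64-121 (58) | 48% | 7 + 3 = 10 | 7 + 21 = 28 |
| 10 | 61-121 (61) | 50% | 10 + 3 = 13 | 10 + 21 = 31 |
| 14 | 57-121 (65) | 54% | 14 + 3 = 17 | 14 + 21 = 35 |

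With a lag of 10-14 days, the unreached time on bupropion is 13-17 days (11-14% of the window) and on any study drug 31-35 days (26-29%).

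**Number exposed.** Section 6.2 aims for about 50% women among 528 participants and section 6.6 allocates 1:1, so 528 × 0.5 × 0.5 = 132 women in the TAU+SCT arm. This is an upper figure, before removing those not of childbearing potential.

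**The case against.** The strongest reply is that the section 17.1 sentence is a routing rule. It says which form a pregnancy goes on and for which conception dates, next to a similar rule for laboratory results, and promises no active testing. A volunteered pregnancy can be entered, so the rule can be followed as written. That is fair as far as it goes: there is no outright contradiction. But a fixed conception window with no way to ascertain conceptions in its last 51 days gives a count that cannot be relied on.

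Second, Table 2 may not show every prompt. The adverse event follow-up after week 10 is not marked in it either, and the pregnancy CRF and the data center's completion guidelines are not available here. A prompt could exist in them. Still, the visit schedule is the protocol's own, and it contains none.

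Third, 42% overstates the exposure that matters. The Table 1 rationale concerns bupropion; 48 of the 51 days are after bupropion, 30 are after all study drug, and the TAU arm receives none. Without an assumed test lag the bupropion gap is 3 days. This stands, and is why the split by drug exposure is shown. It limits the consequence but does not remove the gap, since the protocol itself chose to run the window to day 121.

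Finally, stopping routine tests at the end of active treatment is a defensible choice, given the contraception agreement at entry and three scheduled tests. That argues against requiring further tests, not against asking one question.

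**Conclusion.** The concern holds. The protocol sets a conception window to day 121, and its schedule neither tests for nor asks about pregnancy after week 10. By calendar alone, 51 of 121 days (42%) are uncovered, or 57 days (47%) if the last test is on day 64. Of the 51 days, 21 overlap the tapers and 30 are off study drug. The longer exposure figures depend on the assumed test lag. The number of pregnancies missed cannot be estimated from the document.

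The conclusion rests on reading Table 2 as the full list of visit assessments; a prompt in the CRF or its completion guidelines would close the gap in practice, and should then be stated in the protocol. The effect is on safety ascertainment only: the primary analysis, sample size and error rate do not change. It should be corrected because correction is cheap.

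**What to change.** Add to section 6.5.3 and Table 2, for female participants at weeks 16 and 28, one question: any pregnancy since the last visit and, if so, the estimated conception date. A positive answer triggers the pregnancy CRF.

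The week-28 question covers the whole window for those who attend. Days 190-196 fall 190 − 121 = 69 to 196 − 121 = 75 days after it closes. Even if the full 21-day frame falls before the nominal date, the margin is 190 − 21 − 121 = 48 days. The week-16 question gives earlier notice and some protection against loss to follow-up.

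Optionally, run a urine pregnancy strip on the week-16 drug-screen sample. With an assumed 14-day lag it reaches conceptions to day 106 − 14 = 92 through 112 − 14 = 98. That is past the end of the inhaler taper (day 91) but short of day 121, so it supplements the question and does not replace it.

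The cost is one CRF item at two existing visits and, if the strip is used, the 2 minutes Table 2 allots to a pregnancy test. No extra visit, staff or change to the analysis is needed.

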7.0 STUDY PROCEDURES

7.1 Study Overview

Table 2 provides an overview of the participant procedures and assessments.

Assessment/ Procedure	Time Est (Min)	Scrn/ Base		Active Treatment Phase								FU		
			1	2	3	4	5	6	7	8	9	10	16	28
Bupropion XL	5		Х	Х	X	Х	Х	Х	Х	Х	Х	Х		
Smoking Cessat. Counseling	10		Х	Х	Х	Х	Х	Х	Х	Х	Х	Х		
Nicotine Inhaler	5				Х	Х	Х	Х	Х	Х	Х	Х		
Contingency Management	15					2X								
Screening Assessments					ſ		ĺ							
Informed Consent	30	X*												
Demographics	5	X*												
Smoking History Survey	10	X*												
CIDI	90	X*												
Blood chemistry	2	X*												
Birth Control Assessment	2	X*												
ECG	15	X*												
Medical History & Addendum	15	X*												
Substance Abuse Tx Status	5	X*												
Physical Exam	20	X*												
Safety Assessments														
Vital Signs	5	\mathbf{X}^+	Х	Х	Χ	Х	Х	Х	Х	Х	Х	Х		
Weight	1	X*					Х					Х		
Urine Pregnancy Test	2		X*				Χ					Χ		
Adverse Events	5	X*	Χ	Х	Χ	Χ	Χ	Χ	Χ	Χ	Х	Χ		
Prior/Concom Meds	5	X*	Χ	Х	Χ	Χ	Χ	Χ	Χ	Χ	Х	Χ		
HADS	2	X*	Χ	Х	Χ	Χ	Χ	Χ	Χ	Χ	Х	Χ		
Pittsburgh Sleep Quality Index	5	X*					Х					Х		
PRISM -Suicide and Homicide	5	X*					Х					Х		
Efficacy Assessments														
Urine for UDS	2	X^+	2X	2X	2X	2X	2X	2X	2X	2X	2X	2X	Χ	Χ
ASI-Lite	45	X*												
ASI-Lite Follow-up	30											Χ	Χ	Χ
Timeline Follow-Back	10	X*	2X	2X	2X	2X	2X	2X	2X	2X	2X	2X	Х	Χ
Risk Assessment Battery	15	X*										Χ	Х	Χ
BSCS	2	X*	Χ	Х	Χ	Χ	Χ	Χ	Χ	Χ	Χ	Χ	Χ	Χ
CO level	2	X^+	2X	2X	2X	2X	2X	2X	2X	2X	2X	2X	Χ	Χ
Other Assessments														
Fagerström (FTND)	2	X*										Χ	Χ	Χ
Locator Information	5-10	X*										Χ	Χ	
Study Questionnaire	5	X*											7	

Table 2 Overview of Study Assessments and Procedures

CTN-0046 Protocol Version 5.0 – 10-12-11

Assessment/ Procedure	Time Est (Min)	Scrn/ Base		Active Treatment Phase								F	U	
			1	2	3	4	5	6	7	8	9	10	16	28
Thoughts about Abstinence	6	X*										Х		
Withdrawal Scale Tobacco	1	X*				Х	Х	Х	Х	Х	Х	Χ		
Compliance – Medication	5			Х	Х	Х	Х	Х	Х	Х	Х	Х		
Non-study Smoking Tx	1		Х	Х	Х	Х	Х	Х	Х	Х	Х	Х	Х	Х
Assessment Time Est. (min)*		340 [♠]	40	43	43	44	57	44	44	44	44	115	69	64
Administrative Forms														
Study Eligibility	15	X*												
Randomization	5	X*												
Treatment Tracking Form	10		Х	Х	Х	Х	Х	Х	Х	Х	Х	Х		
Compliance – Smk Counseling	2		Х	Х	Х	Х	Х	Х	Х	Х	Х	Х		
CM Tracking Form	5					2X								
End of Treatment Status	5											Χ		

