8.3 Dispensing Study Medication

Starting in study week 1 and continuing through study week 9, bupropion XL will be dispensed weekly to the TAU+SCT participants for daily self-administration. At the week 10 visit, TAU+SCT participants will be provided with a 3-day bupropion XL dose taper, in which 150 mg is taken once per day. Starting in study week 3 and continuing through study week 9, nicotine cartridges will be dispensed weekly to the TAU+SCT participants for daily self-administration. During week 10, the TAU+SCT participants will receive nicotine cartridges for the 3 week taper.

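### Appendix A runs adverse-event assessment to 30 days after the last active visit, but Table 2 schedules none after week 10, so new non-serious events in the taper period are not systematically elicited

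*Protocol*

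**What the plan says.** Three places in the Protocol together determine when AEs are collected.

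- **Appendix A, section 17.1** gives the time span: AE assessment starts at consent, and "follow-up will continue through 30 days post last active treatment visit". The sentence before it gives the method: "Qualified research staff will elicit participant reporting of reportable AEs/SAEs at study assessment visit designated to collect AEs".
- **Section 6.5.3, item 1** says where the schedule is set: "AEs will be assessed by study staff as outlined in Table 2".
- **Table 2 (section 7.1)** marks the 5-minute AE item at screening/baseline and once in each of weeks 1 to 10. The week 16 and week 28 columns are blank in that row.

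Section 7.5 places the two follow-up visits at approximately weeks 16 and 28, each with a 21-day timeframe. No visit, telephone call or other AE contact is described between week 10 and the first of these.

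Study drug use in the TAU+SCT arm goes on past the last AE assessment. Sections 7.4, 8.3 and 8.10.1 provide a 3-day bupropion XL taper from the final week-10 visit. For the inhaler, section 8.3 says: "During week 10, the TAU+SCT participants will receive nicotine cartridges for the 3 week taper".

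Section 11.3.3 compares AE and SAE incidence between arms and states no time period for the AE tables.

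**The concern.** Appendix A states an AE span that the visit schedule cannot deliver. A site that follows Table 2 exactly asks its last AE question at week 10. It then hands TAU+SCT participants up to three weeks of further study drug and does not see them for a study purpose until the stated window has closed.

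New non-serious events that start during the tapers, or in the first days after drug is stopped, reach the database only if somebody happens to report them. Sites may also handle such reports differently, because one part of the Protocol says the window is open and another provides no occasion to ask. The analyst preparing the section 11.3.3 tables then has no clear rule on whether events with onset after week 10 belong in them.

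**Working it through.** **Step 1. Are the blank AE cells real, or lost in the text conversion?** Table 2 prints a total assessment time per visit, so the rows can be re-added. The convention that reproduces every printed total is: TLFB once per week at 10 minutes, UDS and CO at 2 × 2 = 4 minutes in weeks with two visits, and locator information at 5 minutes (the lower end of its 5–10 range).

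- Weekly core: vital signs 5 + AE 5 + medications 5 + HADS 2 + UDS 4 + TLFB 10 + BSCS 2 + CO 4 + non-study smoking treatment 1 = 38.
- Week 1: 38 + pregnancy test 2 = 40 (printed 40).
- Weeks 2 and 3: 38 + medication compliance 5 = 43 (printed 43).
- Weeks 4 and 6 to 9: 43 + withdrawal scale 1 = 44 (printed 44).
- Week 5: 44 + weight 1 + pregnancy test 2 + PSQI 5 + suicide/homicide screen 5 = 57 (printed 57).
- Week 10: 57 + ASI-Lite 30 + RAB 15 + FTND 2 + locator 5 + thoughts about abstinence 6 = 115 (printed 115).
- Week 16: UDS 2 + ASI-Lite 30 + TLFB 10 + RAB 15 + BSCS 2 + CO 2 + FTND 2 + locator 5 + non-study treatment 1 = 69 (printed 69).
- Week 28: the same without the locator form, 69 − 5 = 64 (printed 64).

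On this convention all 12 totals reproduce. Weeks 1 to 10 match with the AE item in, and weeks 16 and 28 match with it out. Adding it would give 69 + 5 = 74 and 64 + 5 = 69. Week 28 is the cleanest check, since nothing in it is doubled or given as a range. The blanks are the plan's own.

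**Step 2. Where does the 30-day window fall?** The active phase is 10 weeks (section 7.4). Assume the last active visit is on day 10 × 7 = 70.

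| Event | Calculation | Study day (approx.) |
|---|---|---|
| Last scheduled AE assessment | 10 × 7 | 70 |
| Bupropion XL taper ends | 70 + 3 | 73 |
| Inhaler taper ends | 70 + 21 | 91 |
| Appendix A window closes | 70 + 30 | 100 |
| Week 16 | 15 × 7 + 1 to 16 × 7 | 106–112 |

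Scheduled AE assessments from day 71 to day 100: none. The inhaler taper fills 21 of those 30 days. From week 10 to week 16 is nominally 6 × 7 = 42 days. The true interval varies, because section 7.5 gives a 21-day timeframe without saying where it sits around the nominal week.

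**Step 3. What still reaches the database?** Appendix A requires deaths that come to the investigator's attention during follow-up to be reported (17.1). It requires SAEs to be reported within 24 hours of site knowledge, and followed with reporting through the follow-up period (17.3). These routes depend on the site learning of the event. None of them asks every participant about new non-serious events.

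**The case against.** The strongest reply is that the Appendix A sentence uses two terms: assessment starts at consent, and follow-up continues to day 30. Elsewhere section 17.1 uses follow-up for unresolved events that were already reported. One could therefore read the plan as eliciting new events through week 10 and tracking known ones for 30 days more, in which case Table 2 contradicts nothing. This reading is possible but fits poorly. The same paragraph separately has reportable events followed until resolution, stabilization or study end, so a 30-day limit on known events would be redundant or in conflict with it. Even on this reading, no contact is scheduled in the 30 days.

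A second reply is that the treatment programs watch their patients (section 12.5.4) and that Appendix A has staff review AEs when participants attend. But inclusion criterion 6 requires scheduled treatment for only 10 weeks after randomization, so later attendance is not assured.

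Other parts of the reply stand, and they rule out stronger conclusions that a reader might draw:

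- *That post-week-10 events go wholly unrecorded.* They do not. Deaths and SAEs known to the site are reported.
- *That the between-arm AE comparison is biased.* Ascertainment follows the same schedule in both arms over weeks 1 to 10, so the comparison for that period is valid. The documents give no basis for sizing an undercount afterwards.
- *That the concomitant-medication row is also contradictory.* Section 6.5.3 limits that record to the period before and during the active study, which Table 2 can be read as matching.
- *That the pregnancy window to study day 121 shows how the plan counts exposure.* The Protocol never derives that figure, and it concerns pregnancies.

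**Conclusion.** The concern holds as a mismatch between Appendix A on one side and section 6.5.3 with Table 2 on the other. The stated span reaches 30 days past the last active visit, and the schedule provides no AE assessment in those days. All 3 days of the bupropion XL taper and all 21 days of the inhaler taper fall in that gap, in the TAU+SCT arm only. The loss is systematic elicitation of new non-serious AEs during the tapers and the early post-treatment days. The primary endpoint is not affected, nor is the validity of the on-treatment safety comparison.

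The day counts assume a last active visit at day 70 and a week-16 visit in its nominal week. The conclusion that no AE assessment is designated after week 10 needs neither assumption. It should be corrected, since the change is small and sites cannot deliver the Appendix A span from Table 2 as it stands.

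**What to change.** Reconcile section 6.5.3, Table 2 and Appendix A 17.1.

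1. Mark the AE form in Table 2 at the existing week-16 visit, in both arms, so that ascertainment stays symmetric.
2. Ask about events with onset from the week-10 visit through 30 days after it.
3. State in section 11.3.3 that these events are tabulated by arm, separately from the weeks 1 to 10 comparison.

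The cost is a table edit and about 5 minutes per participant, taking the week-16 total from 69 to 74 minutes. Because week 16 falls after the window closes, collection is retrospective, with recall of up to about six weeks (nominal, given the 21-day timeframe). Participants who miss week 16 contribute nothing. If recall is judged too weak, the alternative is one added contact by about day 100, at greater cost to sites. The concomitant-medication form, also 5 minutes, is at most an optional companion.

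If the sponsor in fact intends new events to be elicited only through week 10, Appendix A should say so and limit the 30 days to events already recorded, with the means of contact named.
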